- Oral, rectal, axillary, or tympanic temperature $\geq 38.3^{\circ}\text{C}$ (100.9°F), confirmed by repeat measurement after at least 15 minutes, in the 24 hours preceding the Outcome Assessment Visit or measured at the Outcome Assessment Visit, unless attributed to a new process that is unrelated to the prior diagnosis of pneumonia;
- Elevated respiratory rate (RR >50 breaths/minute for children <24 months of age and >40 breaths/minute for children 24-71 months of age) at the time of the Outcome Assessment Visit;
- Presence of cough grade 2 or 3 at the Outcome Assessment Visit, (defined in Table 2).

³Solicited events (Table 3) will be captured daily until Outcome Assessment Visit #2; thereafter, parents/legal guardians will report symptoms based on memory aid and medical interview by

study staff. For those with multiple solicited events, the ordinal response table will be based upon the most severe solicited event.

Table 2: Severity of Cough

Symptom	Mild (Grade 1)	Moderate (Grade 2)	Severe (Grade 3)
Cough	Occasional coughing (less than 4 times hourly)	Frequent coughing (4 or more times an hour), interferes with sleep)	Almost constant coughing (never free of cough), makes sleep nearly impossible

Table 3. Solicited Events Grading

Symptom	Mild (Grade 1)	Moderate (Grade 2)	Severe (Grade 3)
Irritability	More irritable or fussy than usual but can be consoled; no interference with smiling/playing	Irritability or fussiness that is difficult to console and interferes with smiling and playing	Irritability or fussiness that lasts for more than 4 consecutive hours in a 24 hour period or cannot be consoled
Vomiting	1 episode/day	2-3 episodes/day	≥4 episodes/day
Diarrhea	Looser than normal stools occurring 3-6 times/day	Looser than normal stools occurring >6 times/day	Bloody diarrhea, or diarrhea that requires medical intervention, laboratory testing, or hospitalization
Allergic Reaction	Localized rash or pruritus without rash	Diffuse rash (maculopapular or urticarial)	Generalized rash consistent with Stevens-Johnson Syndrome, erythema multiforme, or toxic epidermal necrolysis; anaphylaxis; or angioedema
Stomatitis	Oral lesions associated with parenteral report of mild oral discomfort	Oral lesions associated with difficulty swallowing, but able to eat and drink	Oral lesions associated with inability to swallow solids or liquids; requires medical intervention, IV fluids, or hospitalization

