- Oral, rectal, axillary, or tympanic temperature $\geq 38.3^{\circ}\text{C}$ (100.9°F), confirmed by repeat measurement after at least 15 minutes, in the 24 hours preceding the Outcome Assessment Visit, unless attributed to a new process that is unrelated to the prior diagnosis of pneumonia;

- Elevated respiratory rate (RR >50 breaths/minute for children <24 months of age and >40 breaths/minute for children 24-71 months of age) at the time of the Outcome Assessment Visit;

- Presence of cough grade 2 or 3 at the Outcome Assessment Visit, defined as Grade 0 (no cough), Grade 1 (Occasional coughing [less than 4 times hourly]), Grade 2 (frequent coughing [4 or more times an hour], interferes with sleep), Grade 3 (almost constant coughing (never free of cough), makes sleep nearly impossible);

³ Solicited events will be captured daily until Outcome Assessment Visit #2; thereafter, parents/legal guardians will report symptoms based on memory aid and medical interview by study staff. For those with multiple solicited events, the ordinal response table will be based upon the most severe solicited event.

Day 1: Day 1 begins at the time the first dose of study product is administered and ends at 11:59 PM of that same day. If a subject has no recorded receipt of study product at the time of the analysis, then Day 1 will be defined as the date 5 days after the date of initiation of the initial antibiotic.

DOOR at Outcome Assessment Visit #1: Defined as above, using DOOR components from the following Study Days.

Adequate Clinical Response: Day 1 – Day 5

Resolution of Symptoms:

- o Fever as measured in the 24 hours prior to Outcome Assessment Visit #1. If a subject has a fever according to a single measurement, but no repeat measurement after at least 15 minutes has been performed, the subject will be analyzed as having a fever. If a subject has a fever according to the measurement taken as a part of vital signs

during Outcome Assessment Visit #1, the subject will be analyzed as having a fever at Outcome Assessment Visit #1. If the vital signs measurement shows no fever, and the parental assessment of fever during the previous 24 hours is missing, then fever will be treated as missing.

- o Respiratory Rate and Cough: determined at Outcome Assessment Visit #1

Solicited Events: Day 1 – Day 5

Number of Days of Antibiotic Use: Day 1 – Day 5

DOOR at Outcome Assessment Visit #2: Defined as above, using DOOR components from the following Study Days.

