Adequate Clinical Response: Day 1 – Day 18

Resolution of Symptoms:

- o Fever as measured in the 24 hours prior to Outcome Assessment Visit #2. If a subject has a fever according to a single measurement, but no repeat measurement after at least 15 minutes has been performed, the subject will be analyzed as having a fever. If a subject has a fever according to the measurement taken as a part of vital signs during Outcome Assessment Visit #2, the subject will be analyzed as having a fever at Outcome Assessment Visit #2. If the vital signs measurement shows no fever, and the parental assessment of fever during the previous 24 hours is missing, then fever will be treated as missing.
- o Respiratory Rate and Cough: determined at Outcome Assessment Visit #2

Solicited Events: Day 1 – Day 18

Number of Days of Antibiotic Use: Day 1 – Day 18

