6.5. Missing Data

While all efforts will be made to minimize missing data, some missing data is expected. Whenever possible, subjects terminating from the study early will be given an early termination visit during which the available components of the DOOR and related measures can be recorded. The primary analysis will use multiple imputation with linear models to impute values using available information (treatment, randomization strata variables, and available visit information), assuming a missing at random (MAR) model. Secondary analyses will further examine the robustness of this analysis, including a “worst case analysis” in which all imputations of missing

data will be the worst case (result in the lowest possible DOOR given available information) for subjects in the 5-day arm and best case for subjects in the 10-day arm. Day 1 in this study is defined as the date of first receipt of study product. If a subject has no record of study product administration or did not receive a first dose of study product, but has other post-randomization data, Day 1 will be imputed as the date 5 days after the date of first receipt of initial antibiotic.

In some cases, a subject may have DOOR defined despite missing some of its components, in which case the subject will be eligible for inclusion into the CC and ATP analysis populations. In analyses of the components of the DOOR using the CC and ATP analysis populations, data will be analyzed as available and missing data will not be imputed.

The study includes several composite variables with rules for assignment, missingness, and imputation described below.

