6.5.2. Fever at OAV#1 or OAV#2

Two variables are used to define Fever at OAV#1 or OAV#2:

- ACRTEMP: Has the subject had a recorded temperature > 38.3 °C (100.9 °F) in the past 24 hours? (Yes/No)
- ACRFEV: If Yes, was fever attributed to a process unrelated to the prior diagnosis of pneumonia? (Yes/No)

Fever at Outcome Assessment Visit #1 and Fever at Outcome Assessment Visit #2 both involve several data components and have complex rules for when they are considered missing versus when fever is considered present or not present. The below logic describes the rules. Note that “fever is observed as a solicited event” only if a temperature of ≥ 38.3 °C (100.9 °F) was recorded on the day of the Outcome Assessment Visit or on the day prior to the Outcome Assessment Visit and either had no recorded confirmatory measurement at least 15 minutes after the first measurement or else the confirmatory measurement also indicated a temperature of ≥ 38.3 °C (100.9 °F). Fever at the OAV is never missing if the OAV did occur (specifically, ACRTEMP not missing), and the vital signs measurement at the visit and the actual temperatures reported by parents and recorded on the solicited events form (SRS) are treated as optional and supplemental data in the determination of the presence of fever at the visit.

- If the OAV did occur
 - o If subject had a recorded temperature ≥ 38.3 °C (100.9 °F) (ACRTEMP) and fever is not indicated as unrelated to prior diagnoses of pneumonia (ACRFEV), then fever at the OAV is present

- o If subject had a recorded temperature ≥ 38.3 °C (100.9 °F) (ACRTEMP) and fever is indicated as unrelated to prior diagnoses of pneumonia (ACRFEV), then fever at the OAV is absent
- o If subject had a recorded temperature ≥ 38.3 °C (100.9 °F) (ACRTEMP) and fever is indicated as relatedness to prior diagnoses of pneumonia (ACRFEV) is missing, then fever at the OAV is missing
- o If subject had a recorded temperature < 38.3 °C (100.9 °F) (ACRTEMP), then fever at the OAV is absent

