8.1.1. Primary Analysis of DOOR at Outcome Assessment Visit #1

DOOR at Outcome Assessment Visit #1 is defined in Section 3.3.

The null hypothesis corresponding to the primary analysis of this study is:

H0: The sum of the probability that a subject assigned to the 5-day arm will have a higher DOOR at Outcome Assessment Visit #1 than if assigned to the 10-day arm plus one-half the probability of equal DOORs at Outcome Assessment Visit #1 is 50% (i.e., no difference in DOOR at Outcome Assessment Visit #1).

The above null hypothesis can be tested using a Mann-Whitney U Test (Evans 2015).

The primary analysis will use multiple imputation with a linear model to impute missing DOOR at Outcome Assessment Visit #1 outcomes. Details of multiple imputation methods are described in Section 8.4.1.

For each of the 20 complete multiply imputed datasets, a Mann-Whitney U statistic will be computed using randomization to short course versus randomization to standard course to define the binary grouping and DOOR at Outcome Assessment Visit #1 as the outcome. The U statistics are asymptotically normal distributed, and so they can be combined into a single test statistic using Rubin's Rules (Marshall 2009).

Defining the following:

n_1 : number of subjects in ITT cohort randomized to a short course of antibiotics

n_2 : number of subjects in ITT cohort randomized to a standard course of antibiotics

m : number of imputed datasets ($m = 20$)

Q_i : U statistic computed from the i^{th} multiply imputed dataset

$$\bar{Q} = \frac{1}{m} \sum_{i=1}^m Q_i$$

Q_0 : the expected value of a U statistic under the null hypothesis ($Q_0 = \frac{n_1 n_2}{2}$)

\bar{U} : The within imputation variance (this is not the mean of the U statistics). Correcting for ties, the formula for the within imputation variance of U is:

$$\bar{U} = \text{Var}(Q_i) = \frac{n_1 n_2}{12} \left[(n_1 + n_2 + 1) - \sum_{c=1}^D (M_c^3 - M_c) \right] \quad (\text{Lehmann 1975, Zhao 2008}),$$

where M_c is the number of tied ranks for the c^{th} value DOOR in the dataset and D is the number of distinct values of DOOR in the dataset. Because the numbers of tied ranks should be very similar across the 20 multiply imputed datasets, the number of ties will be counted from the first imputed dataset only, and those counts will be used to compute the corrected variance.

$$B = \frac{1}{m-1} \sum_{i=1}^m (Q_i - \bar{Q})^2$$

$$T = \bar{U} + \frac{m+1}{m} B$$

$$W = \frac{(\bar{Q} - Q_0)^2}{T}$$

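### Two fever definitions feed the primary DOOR: SAP 3.3 counts a febrile reading taken at the visit, the four rules in SAP 6.5.2 do not use it, and nothing says which prevails

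*SAP*

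**What the plan says.** **Definitions that count the visit reading.** Footnote 2 of protocol Table 1 (section 3.2.1) covers the 24 hours before the visit and adds "or measured at the Outcome Assessment Visit, unless attributed to a new process". In SAP 3.3, the derived-variable text for each visit uses the vital-signs temperature. For OAV#1 it begins "If a subject has a fever according to the measurement taken as a part of vital signs" and classes the child as febrile. For OAV#2 it ends "the subject will be analyzed as having a fever at Outcome Assessment Visit #2". If the vital sign is not febrile and "the parental assessment of fever during the previous 24 hours is missing, then fever will be treated as missing". SAP 8.1.1 ties the primary endpoint to this section: "DOOR at Outcome Assessment Visit #1 is defined in Section 3.3".

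**Definition that does not apply it.** SAP 6.5 introduces its subsections with "The study includes several composite variables with rules for assignment, missingness, and imputation described below". Section 6.5.2 then states "Two variables are used to define Fever at OAV#1 or OAV#2". ACRTEMP is a Yes/No item on a recorded temperature above threshold in the past 24 hours. ACRFEV asks whether that fever was attributed to something other than the pneumonia. Visit vital signs and the parental temperatures on the solicited-events form (SRS) are "treated as optional and supplemental data in the determination of the presence of fever at the visit". None of the four rules says how they enter.

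**Where 6.5.2 leads.** SAP 6.5.3 takes fever from 6.5.2 into resolution of symptoms. SAP 6.5.5 assigns OCR 5 when symptoms have not resolved, and 6.5.7 builds DOOR from the OCR. The final fever analysis in SAP 8.2.4 cites 6.5.2, while the third interim DSMB display in SAP 6.6 counts a reading taken at the visit.

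**The concern.** Both sections claim the primary endpoint: 3.3 through the reference in 8.1.1, and 6.5.2 through the derivation chain to the OCR. Two programmers who each follow the SAP could build different primary datasets.

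Fever is one of three symptoms that separate OCR 5 from OCR 1-4. It decides the rank of a child with adequate clinical response, normal respiratory rate and cough grade 0-1. If 6.5.2 makes fever missing for such a child, the OCR is missing as well. The child is then imputed in the ITT analysis and drops out of the complete-case cohort CC-V1, whereas 3.3 would give an observed OCR 5. The same conflict affects DOOR at OAV#2.

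If the choice is left open until the data are unblinded, it could be made with knowledge of its effect.

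**Working it through.** **1. The two sections applied to a child with a febrile visit reading**

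| ACRTEMP | ACRFEV | SAP 6.5.2 | SAP 3.3 | Agree? |
|---|---|---|---|---|
| Yes | No (not unrelated) | present | present | yes |
| Yes | Yes (unrelated) | absent | present by the vital-signs sentence, which has no exception; the Table 1 footnote has one | arguable |
| Yes | missing | missing | present | no |
| No | not asked | absent | present | no |
| missing | not asked | no explicit rule; missing by implication | present | no |

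The sections agree in one state of five and differ in three. One state is arguable.

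**2. Effect on the OCR** (SAP 6.5.5; adequate response, normal respiratory rate, cough 0-1)

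- ACRTEMP No: OCR 5 under 3.3; OCR 1-4 under 6.5.2, by worst solicited event.
- ACRTEMP Yes with ACRFEV missing, or ACRTEMP missing: OCR 5 under 3.3; OCR missing and imputed under 6.5.2.

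**3. Inconsistencies inside 6.5.2**

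- It says fever cannot be missing once ACRTEMP is recorded, yet its third rule makes fever missing when ACRTEMP is Yes and ACRFEV is missing.
- It defines when fever counts as observed from recorded temperatures, including the repeat measurement, but no rule uses that definition.
- The ACRTEMP item is worded >38.3 °C; the rules use ≥38.3 °C.

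**4. Size per child**

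Input: 180 per arm (SAP section 5). The estimate is U/(n₁n₂). Moving one child in one arm changes U by at most the size of the other arm:

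180/(180 × 180) = 1/180 = 0.0056, or 0.56 percentage points. At 200 per arm it is 1/200 = 0.50 points.

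Null standard error without ties: √[(2n + 1)/(12n²)] = √[361/(12 × 180²)] = 0.0305. Ratio: 0.0056/0.0305 = 0.18.

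DOOR is heavily tied, and ties shrink this standard error. Assume, for illustration, OCR 1/2/5 in 90%/5%/5% of both arms with 0 vs 5 antibiotic days. The tied groups are then 162, 162, 9, 9, 9 and 9:

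- Σ(t³ − t) = 8,505,612; divided by 360 × 359 this is 65.81.
- Var(U) = (180²/12) × (361 − 65.81) ≈ 797,006; SE = √797,006/180² = 0.0276.
- One short-course child moved from OCR 1 to OCR 5 loses 171 pairs: 171/32,400 = 0.0053, or 0.19 SE.

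The ratio is therefore roughly 0.2, and the exact value depends on ties.

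**5. Illustrative total**

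The documents give no rate of discordant readings. Assume OCR 1 to 8 in 50/25/10/3/10/1.5/0.5/0% of both arms and 0 vs 5 antibiotic days (base estimate 0.667). Moving children from OCR 1-4 to OCR 5 lowers the estimate as follows:

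| Share moved | Short-course arm only | Both arms equally |
|---|---|---|
| 0.5% | 0.003 | 0.001 |
| 1% | 0.006 | 0.003 |
| 2% | 0.012 | 0.005 |
| 5% | 0.031 | 0.012 |

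The sample size of 360, inflated to 400, does not depend on this point.

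**The case against.** **The main discordant state may be a data discrepancy.** ACRTEMP asks about any recorded temperature in the past 24 hours, and a reading at the visit falls literally within that period. Sites may well answer Yes, and a No beside a febrile vital sign is a natural data query (protocol sections 13 and 15.2 describe such checks). This stands in part, and it shapes the fix. But nothing requires sites to enter the visit reading under ACRTEMP, and no specific check is stated. Protocol 7.3 and 8.1 describe the 24-hour item as parental report or documentation, with the visit temperature taken separately.

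**Other texts also omit the visit reading.** This is true of the SAP's own Table 1 footnote and of the fever wording in the protocol's interim and secondary analysis sections. It shows that the wording varies, not which version governs. If 6.5.2 was meant to narrow the protocol definition, that is undeclared, because SAP section 13 reports no change from the protocol's planned analyses.

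**Inferences that go too far.**

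- That 6.5.2 bars the visit reading altogether. Calling data supplemental does not exclude them; the fault is that no rule says how they count.
- That 6.5.2 is silent when ACRTEMP is missing. Its parenthesis implies that fever is then missing.
- That Listing 17, programmed from the two items only, shows how the endpoint is derived. The listing is titled for the previous 24 hours and fits that title.

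**Conclusion.** The conflict is real and should be settled before unblinding. Following 6.5.2 literally makes fever absent or missing for some children whom protocol Table 1 and SAP 3.3 count as febrile, and no text ranks the two sections.

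The effect on the primary estimate is probably small: at most 0.56 points per reclassified child in one arm of 180, roughly 0.2 null standard errors. The total rests on an unknown count. A reader might infer that the primary result is at material risk of bias. The documents do not support that: treatment is blinded, children had to be without fever at enrolment, and nothing suggests that discordant readings are frequent or concentrated in one arm. The shift is smaller if both arms are affected.

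**What to change.** Put one fever derivation in SAP 6.5.2 and cite it from 3.3, 6.5.3, 6.6 and 8.2.4:

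- **Present** if ACRTEMP is Yes and ACRFEV is No, or if the visit vital sign is ≥38.3 °C (100.9 °F) and is not recorded as unrelated to the pneumonia.
- **Absent** if ACRFEV marks the fever as unrelated, or if ACRTEMP is No and the visit reading is not febrile or not taken.
- **Missing** if the visit reading is not febrile or not taken, and either ACRTEMP is missing or ACRTEMP is Yes with ACRFEV missing.

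These rules give exactly one result for each of the five item states, with or without a febrile visit reading.

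Do not make SRS temperatures a separate trigger: a reading from the day before can be more than 24 hours old. Use SRS temperatures, and a febrile visit reading with ACRTEMP No, only to raise a blinded site query on ACRTEMP and ACRFEV before database lock. The query also lets an unrelated cause be recorded.

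Correct the sentence that says fever cannot be missing, apply or delete the unused definition of observed fever, and align > with ≥. Listings 17 and 18 may stay as listings of the 24-hour item. Report by arm how many children have fever from the visit reading alone.

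The cost is SAP wording, one derivation and some queries; the temperatures are already collected. One downside remains: a visit-only fever from an unrelated illness whose query is not resolved ranks the child 5, as SAP 3.3 already does.

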6.5.3. Resolution of Symptoms at OAV#1 or OAV#2

Resolution of symptoms is defined as the absence of all of the following:

- Fever at the OAV, as defined above
- Elevated respiratory rate (RR >50 breaths/minute for children <24 months of age and >40 breaths/minute for children 24-71 months of age) at the time of the Outcome Assessment Visit (VS1.RESPB);
- Presence of cough grade 2 or 3 at the Outcome Assessment Visit (ACRCGHSV)

If the subject died at any point of participation in the study, then the subject will be analyzed as not having resolution of symptoms at either Outcome Assessment Visit. Otherwise, if the subject did not have adequate clinical response at OAV#1 or OAV#2, then the subject will be analyzed as not having resolution of symptoms at the respective Outcome Assessment Visit(s). Otherwise, if fever, elevated respiratory rate, or presence of grade 2 or 3 cough is indicated at OAV#1 or OAV#2, then the subject does not have resolution of symptoms at the respective Outcome Assessment Visit (regardless of whether some components of the resolution of symptoms are missing). Otherwise, if fever, respiratory rate, and presence of cough are all non-missing and are indicated as 'No' at OAV#1 or OAV#2, then the subject has resolution of symptoms at the respective Outcome Assessment Visit. Otherwise, resolution of symptoms is missing at the Outcome Assessment Visit.

6.5.4. Most Severe Solicited Event at OAV#1 and OAV#2

The maximum severity at OAV #1 will be calculated based on the following rules:

- If a subject has missing data for the severity grade of any solicited event for two consecutive days or has missing data for more than two days from Day 1 to Day 5 then the most severe solicited event at OAV#1 will be missing.
- Otherwise if a subject has missing data for one or two non-consecutive days from Day 1 to Day 5 then the missing severity will be imputed as the maximum severity grade taken across the previous day and the day after the day with a missing severity. As a special case, for subjects missing severity for Day 1, the missing severity will be imputed as the Severity from Day 2. For subjects missing severity at Day 5 but not missing severity at Day 6, the missing severity will be imputed as the maximum of severity gradings from Day 4 and Day 6. For these subjects with severity grades (0 to 3) recorded or imputed for every solicited event (irritability, vomiting, diarrhea, allergic reaction, stomatitis, and candidiasis) from Day 1 to Day 5, inclusive, the most severe solicited event at OAV#1

will be the maximum severity grade taken across all solicited events from Day 1 to Day 5.

- If a subject had any solicited event of severity grade 3 from Day 1 to Day 5, then the most severe solicited event at OAV#1 will be grade 3, regardless of the presence of missing data during that period.

In a similar manner, the maximum severity at OAV #2 will be calculated based on the following rules:

- If a subject has missing data for the severity grade of any solicited event for more than three consecutive days or has missing data for more than five days from Day 1 to Day 18 then the most severe solicited event at OAV#2 will be missing.
- Otherwise if a subject has missing data for five days or less and no more than three of them are consecutive Day 1 to Day 18 then the missing severity will be imputed as the maximum severity grade taken across the previous day and the day after the day with a missing severity. As a special case, for subjects missing severity for Day 1, the missing severity will be imputed as the Severity from Day 2. For subjects missing severity at Day 18, the missing severity will be imputed as the severity from Day 17. For these subjects with severity grades (0 to 3) recorded or imputed for every solicited event (irritability, vomiting, diarrhea, allergic reaction, stomatitis, and candidiasis) from Day 1 to Day 18, inclusive, the most severe solicited event at OAV#2 will be the maximum severity grade taken across all solicited events from Day 1 to Day 18.
- If a subject had any solicited event of severity grade 3 from Day 1 to Day 18, then the most severe solicited event at OAV#2 will be grade 3, regardless of the presence of missing data during that period.

